5.2. Study setting

5.2.1. *Participating health facilities*

This study will be carried out in 11 MOH primary care facilities in two health districts (**Figure 1**). The two health districts were selected in consultation with the MOH and PAHO. Each health district includes one second-level primary health facility (health center) and referring first-level primary health facilities (health posts). A breakdown of these primary care facilities is shown in **Table 1**. Both health districts were sites where the study team previously implemented HEARTS-aligned hypertension control projects. The two health districts were purposefully selected to represent important areas of diversity in Guatemala across location and ethnicity. Neither health district was part of the initial wave of HEARTS implementation in Guatemala (see 5.1: Context of HEARTS implementation in Guatemala). It was also important that each site had motivated MOH leadership.²² The selected health district in Sololá (San Pablo La Laguna) is located in the Central Highlands and has a primarily indigenous Maya population. The selected health district in Chiquimula (Esquipulas) is located in Eastern Guatemala and has a primarily non-Indigenous population. Both health districts have poverty rates of 60-70%²³ with large rural populations.²⁴

Figure 1: Map of study setting

[figure not shown]

Table 1: MOH primary care sites for implementation

Department (health area)	Health district	Health centers, n	Health posts, n	Location	Population of health district	Ethnic group
Sololá	San Pablo La Laguna	1	5	Central Highlands	88,623	94.5% Maya Indigenous
Chiquimula	Esquipulas	1	4	Eastern Guatemala	55,556	96.3% non-Indigenous
Total		2	9			

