6. OUTCOMES

6.1. Primary outcomes

Primary outcomes will be feasibility and acceptability as defined in the Implementation Outcomes Framework (**Table 2**).³⁸ These outcomes will be assessed using quantitative data, qualitative data, and mixed methods (integrated qualitative and quantitative data). Given the study team's prior experience with HEARTS-aligned projects, the focus of the feasibility and acceptability assessments will be on integrating diabetes into the HEARTS model.

Feasibility is the extent to which a new intervention can be successfully carried out in an organization.³⁸ Among MOH participants, feasibility will be assessed through the four-item Feasibility of Intervention Measure (FIM) questionnaire³⁹ and semi-structured interviews. Among patient participants, feasibility will be assessed using enrollment data.

Acceptability is the stakeholders' perception that a new intervention is agreeable or satisfactory.³⁸ Among MOH participants, acceptability will be assessed using the Acceptability of Intervention Measure (AIM) questionnaire³⁹ and semi-structured interviews. Among patient participants, acceptability will be assessed using follow-up visit data and semi-structured interviews.

Table 2: Measures of feasibility and acceptability and their benchmarks

Measure	Minimum benchmark
Feasibility	
Feasibility questionnaire (FIM) among MOH participants	Median $\geq 3.5^a$
Reasons for perceptions of feasibility/infeasibility	N/A
Number of patient participants with diabetes enrolled per health district ^b	25
Number of patient participants with hypertension enrolled per health district ^b	25
Acceptability	
Acceptability questionnaire (AIM) among MOH participants	Median $\geq 3.5^a$

Table 2: Measures of feasibility and acceptability and their benchmarks

Measure	Minimum benchmark
Proportion of patient participants with subsequent follow-up visit within 3 months (among those enrolled with ≥ 3 months remaining in pilot)	75%
Reasons for perceptions of acceptability/infeasibility among patient and MOH participants	N/A
Reasons for dropouts among patient participants	N/A

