Primary outcomes in this pilot study are feasibility and acceptability as defined in the Implementation Outcomes Framework. ^a The FIM and AIM scales range from 1 to 5 with higher values implying greater feasibility or acceptability, respectively; scores are averaged within each participant. ^b Enrollment is defined by a patient having at least one clinic visit entered in the DHIS2 or equivalent longitudinal medical record system; a given patient may have both diabetes and hypertension and thus count toward each benchmark. Abbreviations: AIM: Acceptability of Intervention Measure; FIM: Feasibility of Intervention Measure; MOH: Ministry of Health.	

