6.2. Secondary outcomes

Secondary outcomes include clinical outcomes, implementation outcomes, and patient-related outcome measures (**Table 3**).

Clinical effectiveness outcomes are based on recommended HEARTS monitoring indicators.^{37,40} Clinical outcomes are assessed to provide pilot data to key MOH stakeholders and to rehearse study procedures rather than to evaluate effectiveness.

Implementation outcomes³⁸ will assess facility-level adoption and the fidelity of implementation of each intervention component.

Patient-related outcomes measures relating to diabetes will be conducted to translate and validate questionnaires in Guatemalan Spanish and Mayan Kaqchikel. Measures include diabetes distress, quality of life, and self-care assessments. We will use validated Spanish or professionally translated Mayan language versions of each instrument. These assessments are exploratory to refine the study team's use of these instruments in rural Guatemala.

Table 3: Outcomes and data sources

Outcome	Description and data sources
Primary outcomes	
Feasibility	FIM questionnaires and MOH data from DHIS2 (quantitative); semi-structured interviews with MOH participants (qualitative)
Acceptability	AIM questionnaires and MOH data from DHIS2 (quantitative); semi-structured interviews with patient and MOH participants (qualitative)
Secondary outcomes	
Clinical outcomes	

Table 3: Outcomes and data sources

Outcome	Description and data sources
Number of patients receiving hypertension medication treatment per month (“hypertension treatment rate”)	MOH data from SIGSA (quantitative)
Number of patients receiving diabetes medication treatment per month (“diabetes treatment rate”)	MOH data from SIGSA (quantitative)
Proportion achieving glycemic control (FBG <115 mg/dl or RBG <160 mg/dl) among patients with diabetes	MOH data from DHIS2 (quantitative)
Proportion achieving control of blood pressure (<130/80 mmHg) among patients with hypertension	MOH data from DHIS2 (quantitative)
Mean SBP and DBP among patients with hypertension	MOH data from DHIS2 (quantitative)
Implementation outcomes	
Adoption	Number of participating health facilities, defined as having enrolled at least one patient with hypertension or diabetes (quantitative); reasons for variation (qualitative)

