8. SAMPLE SIZE CONSIDERATIONS

Primary health facilities. The sample of health facilities will include nine health posts and 2 health centers for a total 11 primary health facilities. No formal sample size calculation was performed.^{62,63} This sample of health facilities and population size of pilot health districts is consistent with recommendations in the HEARTS Implementation Guide.²²

Table 4: Semi-structured interview sample

Actor	Number ^a
Participants with diabetes	10
MOH physicians or physicians-in-training	4
MOH professional nurses	4
MOH auxiliary nurses	10
MOH administrators	2
Total	30

^aThe interview sample will be stratified by sex (target of 50% men and women by actor) and by health district (target of 50% from each health district).

Patient participants. The target sample of patient participants will be approximately 100 individuals, or 50 participants per health district. Based on the study team's prior experience, the

anticipated breakdown is n=45 patients with hypertension only, n=45 with diabetes only, and n=10 patients with both hypertension and diabetes. However, it is possible that the improved clinical services may attract a greater number of patients to MOH care than anticipated for the pilot. Of these, a subsample of 10 participants with low versus high retention levels (defined by number of clinical visits within the study time period) will be selected for semi-structured interviews at the close of the study. To improve understanding of how diabetes can be integrated into the HEARTS hypertension primary care model, we will purposely sample patient participants with diabetes.

MOH participants. The anticipated sample of MOH participants working to implement HEARTS will be approximately 50 participants. Of these, a subsample of 20 will be selected for semi-structured interviews at the close of the study using the breakdown shown in **Table 4**.

Including patient and MOH participants, a total of 30 semi-structured interviews are planned to achieve thematic saturation.^{64,65} The interview sample will be sex-stratified with a target of 50% men and women by actor. Interviews will be analyzed as they are conducted, and more may be added if saturation is not achieved.⁶⁶

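### The adoption count pools hypertension with diabetes and health posts with health centers, so 11 of 11 could be reported without showing whether any post enrolled a diabetes patient

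*Combined protocol and SAP*

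**What the plan says.** Table 3 (section 6.2) defines adoption as "Number of participating health facilities, defined as having enrolled at least one patient with hypertension or diabetes", with qualitative explanations of variation alongside. It has no benchmark and no breakdown by disease or facility level.

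Table 2 (section 6.1) has separate rows for "Number of patient participants with diabetes enrolled per health district" and "Number of patient participants with hypertension enrolled per health district", each with a minimum of 25. Its footnote b says "Enrollment is defined by a patient having at least one clinic visit entered in the DHIS2 or equivalent longitudinal medical record system" and lets a patient with both diseases count toward each benchmark.

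On purpose, section 6.1 states that "the focus of the feasibility and acceptability assessments will be on integrating diabetes into the HEARTS model". Section 5.4 says that the components were tested in the team's hypertension projects and that integrated diabetes management is what is new. Section 5.4.2 aims to bring care for both diseases into health posts through task sharing.

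Section 8 gives "nine health posts and 2 health centers for a total 11 primary health facilities" and an expected patient mix of "n=45 patients with hypertension only, n=45 with diabetes only, and n=10 patients with both hypertension and diabetes".

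**The concern.** What the pilot needs to learn is whether diabetes care can be added to the model, including at the posts. The adoption rule is satisfied by one patient with either disease, so a post that only ever registers one hypertension patient counts fully. The benchmarks do not correct for this, because a district's single health center can meet both alone.

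No other row in Tables 2 or 3 fills the gap:

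- Training attendance and care-coordination meetings are counted by district, and report viewing concerns district administrators.
- Medicine and diagnostic availability measures stock, not patients.
- The DHIS2 capture proportion is not split by disease or facility level.
- The monthly treatment rates name each disease but have no stated facility breakdown.

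The results feed scale-up planning (section 12) and the Technical Advisory Committee's strategy work (section 7.3.5). A report of 11 of 11 could be read there as facility-wide uptake of the integrated model, which the count does not measure. At 11 of 11 there is also no variation left for the qualitative part of the adoption row to explain.

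**Working it through.** **Reproducing the plan's figures.** From Table 1, facilities are (1 + 5) + (1 + 4) = 11, of which 2 are centers and 9 are posts. From section 8, patients are 45 + 45 + 10 = 100. Those with diabetes number 45 + 10 = 55, and likewise 55 with hypertension. That is 55 / 2 = 27.5 per district for each disease, against a benchmark of 25.

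**Can every stated criterion be met with no diabetes patient at a post?** Keep the planned mix and 50 patients per district, and give each post one patient with hypertension only.

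| District | Center: diabetes only | Center: hypertension only | Center: both | Posts, one hypertension-only patient each | Total |
|---|---|---|---|---|---|
| San Pablo La Laguna | 22 | 18 | 5 | 5 | 50 |
| Esquipulas | 23 | 18 | 5 | 4 | 50 |

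The overall mix is preserved: diabetes only 22 + 23 = 45; hypertension only 18 + 5 + 18 + 4 = 45; both 5 + 5 = 10.

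Benchmarks:

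- San Pablo La Laguna: diabetes 22 + 5 = 27; hypertension 18 + 5 + 5 = 28.
- Esquipulas: diabetes 23 + 5 = 28; hypertension 18 + 5 + 4 = 27.
- All four are at least 25.

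Adoption:

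- Table 3 rule: 6 of 6 and 5 of 5, so 11 of 11.
- At least one diabetes patient: 2 of 11 (2 of 2 centers, 0 of 9 posts).
- At least one patient of each disease: 2 of 11.

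Only 9 of the 100 patients need be seen at posts.

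**How typical would this be?** The documents cannot say, because they give no post/center split. As an illustration, assume that posts see n of the 100 patients, spread evenly with Poisson counts, and that 55% of them have diabetes as in the overall plan. The expected number of posts with any patient is 9(1 − e^(−n/9)). With any diabetes patient it is 9(1 − e^(−0.55n/9)). The chance that no post has a diabetes patient is e^(−0.55n).

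| Assumed n at posts | Posts adopting, Table 3 rule | Posts with a diabetes patient | Chance that no post has one |
|---|---|---|---|
| 9 | 9(1 − e^−1) = 5.7 | 9(1 − e^−0.55) = 3.8 | e^−4.95 = 0.7% |
| 30 | 9(1 − e^−3.33) = 8.7 | 9(1 − e^−1.83) = 7.6 | e^−16.5, about 7 in 100 million |

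Under these assumptions the two counts differ by one to two posts, and the extreme case is rare.

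**The case against.** The strongest reply is that this is a gap in reporting, not in data, on an outcome that decides nothing. Registries are built at each facility (section 5.4.4), and staff review registration at each facility monthly (section 7.3.2). Physicians audit at least a quarter of visits (section 7.3.6), and 10 of the 20 planned staff interviews are with auxiliary nurses (Table 4). Diabetes has its own benchmark in Table 2 and its own treatment and control rows in Table 3. Adoption is secondary, with no threshold. If the posts' patient mix resembles the overall plan, the rule overstates diabetes uptake by only one or two posts. All of this stands, and it limits the weight of the point. It does not remove the point: none of these sources is specified as a count of diabetes uptake by facility level.

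A second reply is that splitting the count keeps the one-patient threshold, so a post with a single diabetes visit still qualifies. That also stands. Enrolment counts by facility type would show how thin such uptake is.

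A reader might also infer that the rule measures hypertension care already established at these sites, since "Both health districts were sites where the study team previously implemented HEARTS-aligned hypertension control projects". The documents do not support that. They do not say that the earlier work reached these nine posts or that it continues. Section 5.2.2 points the other way: auxiliary nurses do not usually manage drug treatment for either disease, no registry exists, and national HEARTS work has covered hypertension at health centers only. Registering one hypertension patient at a post may itself be new.

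**Conclusion.** The point holds as a mismatch between a stated outcome definition and the pilot's purpose. By the definitions alone, 11 of 11 adoption and all four enrolment benchmarks are compatible with 0 of 9 posts enrolling a diabetes patient. That part rests only on the plan's own facility numbers, case mix and rules.

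How far the reported figure would mislead in practice is unknown. A reader might infer a large gap by supposing that few post patients have diabetes; for example, 30 patients at posts with 20% diabetic would give 9(1 − e^−0.67) = 4.4 posts. Neither the 30 nor the 20% comes from the documents, so this is not evidence of size. Nor do the documents support reading the all-or-nothing case as the expected one, or saying that the pilot could not find out how far diabetes care reached the posts.

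The consequence is a potentially misleading input to scale-up planning. No formal decision turns on the count. It is worth changing because the change is cheap and answers the question that the pilot poses.

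**What to change.** In Table 3, replace the single adoption count with three:

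- facilities with at least one enrolled patient with diabetes;
- facilities with at least one enrolled patient with hypertension;
- facilities with at least one of each, where a patient with both diagnoses counts toward each disease, as in Table 2 footnote b.

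Give each count separately for health centers (of 2) and health posts (of 9). State that a facility is credited when the qualifying visit was entered at that facility. This matters because section 5.4.2 has prescribers make the initial plan and posts carry it out, so one patient may have visits at both levels.

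Tabulate the Table 2 enrolment counts by facility type as well, leaving the district benchmarks unchanged. Note that patients seen at both levels appear in both rows, so the rows may sum to more than the district total.

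The cost is a wording change and a few rows from the planned DHIS2 registries, with no new data collection. The drawback is that the reported adoption figure may be lower than under the pooled rule.

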5.1. Study design

A single-arm pilot trial over 6 months duration will be carried out in 11 Ministry of Health (MOH)-led primary care facilities. A single-arm design was chosen as most appropriate to evaluate feasibility and acceptability and to align with recommendations for pilot projects in the HEARTS Implementation Guide.²²

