5.4.2. Team-based care and task sharing

To implement hypertension and diabetes care in health posts, we will implement a team-based, task-sharing care model between auxiliary nurses staffing health posts and prescribing clinicians (i.e., physicians or professional nurses) at health centers. This intervention component was implemented in the study team's prior hypertension project and has been approved by the MOH.¹⁵ Physicians or professional nurses will make initial patient treatment plans. Auxiliary nurses working in health posts will implement treatment plans by dispensing medications, monitoring glycemic or blood pressure control, and titrating medications under physician supervision. Monthly care coordination meetings will be held in-person or remotely at least once per month to review patient registries and make recommendations for patients whose hypertension or diabetes is not adequately controlled according to MOH guidelines.^{27,28} In our prior projects, monthly meetings have been difficult to operationalize.³⁴ Therefore, we may suggest an alternative approach in which auxiliary nurses at health posts communicate with physicians at health centers in real-time via text messages or phone calls to make treatment changes for uncontrolled patients.

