Fidelity (health worker training on hypertension and diabetes treatment protocols)	Proportion of health workers in each district attending all training sessions, chart audit of prescriptions to assess guideline concordance (quantitative); reasons for variation (qualitative)
Fidelity (team-based care and task sharing)	Proportion of primary health districts conducting at least one care coordination meeting; reasons for variation (qualitative)
Fidelity (access to medicines and diagnostics)	Monthly availability of MOH medications and diagnostics (quantitative) and reasons for variation (qualitative)
Fidelity (facility-based electronic monitoring tool)	Proportion of patient visits captured in DHIS2 each month compared to comprehensive records in SIGSA (quantitative) and reasons for variation (qualitative)
Fidelity (systems monitoring and feedback)	Proportion of quarterly reports viewed by health district administrators (quantitative) and reasons for variation (qualitative)
Usability (facility-based electronic monitoring tool)	System Usability Scale ^{41,42} (quantitative) and reasons for variation (qualitative)
Sustainability	Program Sustainability Assessment Tool (PSAT) ^{43,44} and Clinical Sustainability Assessment Tool (CSAT), ^{45,46} select questions

Table 3: Outcomes and data sources

[figure not shown]
Outcome	Description and data sources
Patient-related outcomes measures	
Diabetes distress	Diabetes Distress Scale (DDS), ^{47,48} 2-item screening and physician distress subscale
Disability	WHO Disability Assessment Schedule (WHODAS 2.0) ⁴⁹
Multimorbidity treatment burden	Multimorbidity Illness Perceptions Scale (MULTIPleS), ^{50,51} treatment burden subscale

Abbreviations: CSAT: Clinical Sustainability Assessment Tool; DBP: diastolic blood pressure; DHIS2: District Health Information System; FBG: fasting blood glucose; MOH: Ministry of Health; PSAT: Program Sustainability Assessment Tool; RBG: random blood glucose; SBP: systolic blood pressure; SIGSA: Health Management Information System; WHO, World Health Organization.

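### No quantitative outcome is defined for treatment delivered at health posts: team-care fidelity records only whether each of two districts held one coordination meeting

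*Combined protocol and SAP*

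**What the plan says.** Section 5.4.2 sets out the component. A physician or professional nurse makes the initial treatment plan. Auxiliary nurses at the health posts then dispense drugs, monitor glucose or blood pressure control, and titrate with a physician supervising. Section 5.2.2 notes that auxiliary nurses do not usually manage these diseases with drugs, so this is a change of practice.

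On coordination, section 5.4.2 says: "Monthly care coordination meetings will be held in-person or remotely at least once per month to review patient registries". It then reports that such meetings were hard to run in earlier projects, and continues: "we may suggest an alternative approach in which auxiliary nurses at health posts communicate with physicians at health centers in real-time via text messages", or by phone.

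Section 6.2 states that the implementation outcomes are to cover the fidelity of every component. For this one, the Table 3 entry is "Proportion of primary health districts conducting at least one care coordination meeting", with qualitative reasons for variation. The nearest other measure, adoption, is "Number of participating health facilities, defined as having enrolled at least one patient with hypertension or diabetes".

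Section 5.2.1 gives the units: "This study will be carried out in 11 MOH primary care facilities in two health districts". Section 8 gives the split: "The sample of health facilities will include nine health posts and 2 health centers for a total 11 primary health facilities".

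**The concern.** The measure does not match the component. The component is three tasks carried out at the posts; the measure is an event at district level that can take place without any of them. It also leaves out the coordination route that section 5.4.2 offers in case meetings prove hard to hold. It can therefore read high when nothing was shared and low when a great deal was.

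Nine of the 11 facilities are posts, and section 5.2.2 says HEARTS in Guatemala has so far concentrated on hypertension at health centers. Treatment at posts, particularly for diabetes, is thus a main new element that scale-up planning (section 12) would carry forward. Section 11.6 also foresees some posts referring patients to health centers after the trial, so where care is delivered is an open question. Without a count of what the posts did, a favorable feasibility or acceptability result cannot be tied to this component having been delivered.

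**Working it through.** **Inputs.** Two districts (section 5.2.1); nine posts and two centers (Table 1, section 8); six months (section 5.1); at least one meeting per month (section 5.4.2); a district counts once it has held one meeting (Table 3).

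**Consistency.** The plan states no target or sample size for this outcome, so there is no figure to reproduce. The facility count agrees with itself: 9 + 2 = 11, and posts are 9/11 = 82% of facilities.

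**Possible values.** The score is k/2 with k = 0, 1 or 2, so it is 0, 50 or 100%. Planned district-meetings number at least 2 × 6 = 12.

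**Scoring the rule under defined scenarios.**

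| Scenario | Meetings held | Posts treating | Fidelity score |
|---|---|---|---|
| A. Texts or calls replace all meetings; every post active | 0 of 12 | 9 of 9 | 0% |
| B. One meeting per district; no task sharing | 2 of 12 (16.7%) | 0 of 9 | 100% |
| C. All monthly meetings; every post active | 12 of 12 | 9 of 9 | 100% |
| D. Sololá: calls only, 5 posts active. Chiquimula: one meeting, no sharing | 1 of 12 (8.3%) | 5 of 9 | 50% |

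B and C cannot be told apart. In D, the district with 5 of 5 posts active fails and the district with 0 of 4 passes.

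**How easily the threshold is met.** Assume each monthly meeting takes place independently with probability m. The documents give no value for m, so a range is shown. P(district counts) = 1 − (1 − m)^6, and P(both count) is its square.

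| m | One district | Both (score 100%) |
|---|---|---|
| 0.1 | 0.47 | 0.22 |
| 0.2 | 0.74 | 0.54 |
| 0.3 | 0.88 | 0.78 |
| 0.5 | 0.98 | 0.97 |

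If three meetings in ten go ahead, a full score is still more likely than not.

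**Whether another outcome fills the gap (Tables 2 and 3, section 7.3).**

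- Adoption needs one enrolled patient, and the Table 2 footnote makes enrollment one recorded visit, with no treatment required.
- The enrollment benchmarks are per district.
- The SIGSA treatment counts and the DHIS2 control outcomes are not specified by facility level.
- Chart audits (section 7.3.6) rate guideline concordance and data entry, not who treated or where.
- Monthly facility visits (section 7.3.2) follow this component through meetings only.

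None of these is defined as treatment at a post.

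**The case against.** This is a mixed-methods pilot, and the same Table 3 row has a qualitative half. Auxiliary nurses account for 10 of the 20 MOH interviews (Table 4), staff visit every facility monthly and keep a field log, and adoption is counted by facility. A reader might infer that the study will learn nothing about the posts. The documents do not support that: participation by posts will be visible, and interviews can describe task sharing. What these sources do not do is quantify delivery.

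A reader might also infer that any district using texts or calls scores zero. That goes too far. The alternative is only something the team may suggest, and remote meetings count. Zero requires no meeting of any kind in six months; a district that meets once and then switches to texts scores full.

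Nor do the documents support the inference that a post treating patients first registered at a health center gets no adoption credit. Enrollment is defined by any recorded visit, and section 5.4.4 plans registries at each facility. At most, the plan leaves unstated which facility is credited when a patient is seen at both levels.

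Finally, the component was used in an earlier hypertension project and approved by the MOH, the stated focus is integrating diabetes, and no benchmark depends on this row. That is a fair reason for a light measure and it limits the severity. It does not justify a measure that scores no delivery and full delivery alike.

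**Conclusion.** The point stands as a mismatch between a component and its fidelity measure. The score has three possible values, gives 100% both for no task sharing and for full task sharing, and gives 0% to full task sharing coordinated wholly by text or phone. No other quantitative outcome covers treatment at the nine posts.

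The scenario scores follow directly from the Table 3 rule; the meeting probabilities are assumptions shown as a range. The defect lies in how the outcome is defined, not clearly in what is collected. The clinical models in section 9 adjust for clustering within facilities, so facility identity should be in the data. The DHIS2 visit and chart audit forms are listed in section 15 but not shown, so whether they already record dispensing site or prescriber contact cannot be checked.

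The outcome is secondary, has no benchmark and drives no stated decision. Severity is minor to moderate.

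**What to change.** Revise the Table 3 row for team-based care and task sharing:

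1. **Coordination by any route.** Count contact between prescriber and auxiliary nurse by meeting, text or call, for example as the share of visits with values above the MOH target that have a recorded prescriber contact.
2. **Delivery at posts.** From DHIS2, by facility, report the number of the nine posts with at least one follow-up treatment visit, defined as a visit after the initial plan at which medication was dispensed or changed on site. Also report the share of each district's follow-up treatment visits that took place at posts.

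Present post-level results as counts rather than percentages: about 100 patients over 11 facilities is roughly 9 each (100/11 = 9.1), too few for stable shares at single posts. State in the adoption row which facility is credited when a patient is seen at both a post and a center.

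Under item 2, scenario A would read 9 of 9 posts instead of 0%, and scenario B 0 of 9 instead of 100%.

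The cost is a rewording of Table 3, one tabulation by facility and possibly one yes/no contact field for health workers to complete. If the existing forms already hold site and contact, no new data entry is needed.
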